4.2.2.2 Restrictions on diet and life style

No restrictions on diet or life style.

4.2.2.3 Contraception requirements

For tiotropium, no clinical data on exposed pregnancies are available. Preclinical studies do not indicate direct or indirect harmful effects with respect to pregnancy, embryonal / foetal development, parturition or postnatal development.

Clinical data from nursing women exposed to tiotropium are not available. Based on lactating rodent studies, a small amount of tiotropium is excreted into breast milk. Therefore, tiotropium should not be used in pregnant or nursing women unless the expected benefit outweighs any possible risk to the unborn child or the infant. Pregnant and nursing women are generally excluded from tiotropium clinical trials.

Clinical data on fertility are not available for tiotropium. A non-clinical study performed with tiotropium showed no indication of any adverse effect on fertility.

Woman of childbearing potential (WOCBP) (for the definition please refer to [Section 3.3.3.](#)) and men able to father a child must use two medically approved methods of birth control throughout the trial, and for a period of at least 30 days after last trial drug intake. They must use one barrier method, i.e. condom or occlusive cap with spermicide, or vasectomized partner, and one highly effective non-barrier method including oral, injected or implanted hormonal contraceptives, intrauterine device or system.

Male patients:

Men whose partner is a WOCBP must use a condom during the study, and for a period of at least 30 days after the last dose of study drug.

Female patients:

WOCBP must use a highly effective method of birth control per ICH M3 (R2) that results in a low failure rate of less than 1% per year when used consistently and correctly during the study, and for a period of at least 30 days after the last dose of study drug.

Acceptable methods of birth control for this trial are:

- Combined (estrogen and progestogen containing) hormonal birth control that prevents ovulation (oral, intravaginal, transdermal).
- Progestogen-only hormonal birth control that prevents ovulation (oral, injectable, implantable).
- Intrauterine device (IUD) or intrauterine hormone-releasing system (IUS).
- Bilateral tubal occlusion
- Vasectomised sexual partner with documented absence of sperm.

Or

Patients must abstain from male-female sex. This is defined as being in line with the preferred and usual lifestyle of the patient. Periodic abstinence e.g. calendar, ovulation, symptothermal, post-ovulation methods; declaration of abstinence for the duration of exposure to study drug; and withdrawal are not acceptable.

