16. Patients who regularly use daytime oxygen therapy for more than 1 hour per day and in the investigator's opinion will be unable to abstain from the use of oxygen therapy.
17. Pregnant or nursing women or women of childbearing potential not using a medically approved means of contraception (i.e., oral or injectable contraceptives, intrauterine devices (IUD) or diaphragm with spermicide, or Norplant®).
18. Significant alcohol or drug abuse within the past 12 months
19. Known hypersensitivity to anticholinergic drugs, lactose, benzalkonium chloride (BAC), ethylenediaminetetraacetic acid (EDTA) or any other components of the HandiHaler® or Respimat® inhalation solution delivery system.
20. Patients currently in any pulmonary rehabilitation program or scheduled to participate in any such program during the study period.
21. Previous participation in this study. (The patient cannot re-enroll into this study.)
22. Patients who are currently participating in another interventional study.

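### Exclusion 17 admits a woman using only a diaphragm with spermicide, which Section 4.2.2.3 does not accept; the two rules for women in 4.2.2.3 also conflict, and its pointer to a definition is empty

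*Protocol*

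**What the plan says.** Protocol 3.3.3, criterion 17, excludes pregnant or nursing women and "women of childbearing potential not using a medically approved means of contraception". It spells out which means count in a list joined by *or*: oral or injectable contraceptives, "intrauterine devices (IUD) or diaphragm with spermicide", or Norplant. Any one of these is enough to enter.

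Protocol 4.2.2.3 governs conduct during the trial and for at least 30 days after the last dose. Its general paragraph covers both women of childbearing potential and men able to father a child. They "must use two medically approved methods of birth control throughout the trial", and the pair is specified: "They must use one barrier method, i.e. condom or occlusive cap with spermicide, or vasectomized partner, and one highly effective non-barrier method", the latter including hormonal contraceptives and intrauterine devices or systems. The same sentence starts with a pointer, "Woman of childbearing potential (WOCBP) (for the definition please refer to" Section 3.3.3.

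The later paragraph on female patients reads differently: "WOCBP must use a highly effective method of birth control per ICH M3 (R2"), with a failure rate below 1% per year. The list that follows has combined hormonal methods, progestogen-only hormonal methods, an intrauterine device or system, bilateral tubal occlusion, and "Vasectomised sexual partner with documented absence of sperm". After a separate *Or* comes abstinence: "Patients must abstain from male-female sex".

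**The concern.** The entry rule and the conduct rule should lead a site to the same answer about the same woman. Here they do not. Someone relying on a diaphragm alone passes eligibility and is out of line with 4.2.2.3 from her first dose unless her contraception changes.

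Within 4.2.2.3, a site cannot tell whether one highly effective method is enough. One site could accept an IUD alone and another could call it a deviation. The term that triggers all of this, childbearing potential, is not defined where the protocol says it is. It also decides who has the urine pregnancy tests in Protocol 5.2.3, and at ages 40 to 80 menopausal or sterilised status is what settles it.

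The protocol states that no clinical data on exposed pregnancies exist and advises against use in pregnancy unless benefit outweighs risk. Having set a contraception rule on that basis, it should set one that can be applied consistently.

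**Working it through.** No power, error rate or sample size is involved. The check is to take each method and read it against the three texts.

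| Method used | Exclusion 17 (3.3.3) | Two-method rule (4.2.2.3) | Female-patient rule (4.2.2.3) |
|---|---|---|---|
| Diaphragm with spermicide alone | may enter | not met; at most the barrier half, if an occlusive cap is read to cover it | not met; not listed |
| IUD alone | may enter | not met | met |
| Oral contraceptive alone | may enter | not met | met, if hormonal and ovulation-preventing |
| Injectable or Norplant alone | may enter | not met | met, if read as the listed progestogen-only forms |
| Tubal occlusion alone | shut out, read literally | not met | met |
| Vasectomised partner alone | shut out, read literally | not met; barrier half only | met |
| Abstinence | shut out, read literally | no such option | met |
| IUD plus condom | may enter | met | met |

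Three results follow.

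1. Of the methods exclusion 17 names, the diaphragm is the only one that, used alone, fails both rules in 4.2.2.3 on any reading.
2. The two rules for women give different answers for a vasectomised partner and for abstinence. The partner is the barrier half of a pair in one rule and sufficient alone in the other. Abstinence appears only in the second.
3. The last row shows that the two rules can be met together.

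On the definition, the criteria in 3.3.3 run from 1 to 22 without a gap or a redaction mark. The term occurs only in criterion 17, undefined. The abbreviation list merely expands the acronym.

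On size, the documents do not say how many women of childbearing potential are expected. With assumed shares:

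- Women of childbearing potential, 0% to 5% of the 71 randomised: 71 × 0 = 0 to 71 × 0.05 = 3.55.
- Diaphragm-only users, 0% to 10% of those: 0 to 3.55 × 0.10 = 0.36.

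**The case against.** The best defence is that an entry screen and a conduct rule do different jobs, and a stricter conduct rule is not in itself a contradiction. That stands in part, since a diaphragm-only user can comply by adding or changing a method. But nothing in the eligibility check prompts it. The review before randomisation in Protocol 6.2.2 goes back to the same criterion 17 and would pass her again.

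A second defence is that the female-patient paragraph only specifies the highly effective half of the required pair. This has some force, because both texts use that phrase, so the mere count of two methods against one is not firm evidence of conflict. It fails on two items. A vasectomised partner belongs to the barrier half under the general rule, and abstinence makes no sense as half of a pair.

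A reader might infer more than the text supports:

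- That the two rules are incompatible. They are not, because an IUD or a listed hormonal method plus a condom satisfies both.
- That men face the same conflict. The condom sentence can be read as the man's own share of the two methods.
- That patients are exposed to material risk. Preclinical studies gave no sign of harm, pregnancy is tested at screening and Visit 4 (Protocol 5.2.3), and exposure in pregnancy is reported within 24 hours and followed to outcome (5.2.6.2.4).

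**Conclusion.** The point holds as an inconsistency in an operative safety rule. Exclusion 17 is wrong as written, because it names a method that 4.2.2.3 does not accept alone. The two rules for women conflict without being incompatible, and the reference to a definition in 3.3.3 is empty.

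The practical effect is very small. On the assumed shares it concerns 0 to 3.6 women for the conflicting rules and 0 to 0.4 for the diaphragm. Neither share comes from the documents, and only the age range of 40 to 80 supports expecting low numbers.

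The analysis is unaffected. Among the exclusion criteria, the SAP's working list of important deviations (Table 6.2: 1) names only 1, 2 and 3, and it removes nobody from an analysis set for them. Correcting the wording is worthwhile because it costs little.

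**What to change.** Reword the contraception part of exclusion 17 to: *women of childbearing potential who do not meet the contraception requirements for female patients in Section 4.2.2.3*. A diaphragm alone then no longer qualifies.

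Have the sponsor's clinical team choose one rule for women, either one listed highly effective method or abstinence, or two methods. State only that rule in 4.2.2.3. This is a clinical choice, since the one-method rule lowers what the general paragraph now demands. That paragraph also covers men, so any deletion must say what remains for them; as it stands, only the condom rule would be left.

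Write the definition of childbearing potential into 3.3.3 and keep the cross-reference whichever rule is chosen. The pointer now sits inside the two-method sentence, so it must be moved if that sentence goes.

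The cost is a wording amendment with matching patient information. A diaphragm-only user must add or change a method. If the one-method rule is kept, women relying on tubal occlusion, a vasectomised partner or abstinence, whom exclusion 17 shuts out if read literally, become eligible. If two methods are kept, women using a single method must add another.

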4.3 TREATMENT COMPLIANCE

The patient will enter, in the Patient Diary, the number of puffs or capsules of study medication taken. The investigator/study staff will review these records with the patient at each study visit to assess treatment compliance. The investigator / study staff should also examine the inhalers used since last visit. The Tiotropium Respimat® dose indicator should concur with the patient diary. And the residual of Tiotropium Handihaler® should be in accord with the patient diary. If compliance rate is not between 80-120%, site staff will explain to the patient the importance of treatment compliance, and the reason of non-compliance should be recorded in the source document. CTM should be notified if patients continue to be non-compliant. Patients will be asked to return all used and unused study medication to the clinic at each scheduled visit and at the end of study.

The study site must transfer data regarding study medication use and rescue medication from Patient Diary to the eCRF within 1 week after each visit.

5. ASSESSMENTS

5.1 ASSESSMENT OF EFFICACY

5.1.1 Primary endpoint

The primary endpoint for patient preference is the performance domain of the Patient Satisfaction and Preference Questionnaire (PASAPQ).

The PASAPQ is a two-part questionnaire. Part I consists of 14 questions. The first 13 questions generate the Performance domain (7 questions) and the Convenience domain (6 questions), which form a Total Score (all 13 questions). Question 14 asks for overall satisfaction with the device used in the study. Part II consists of stand-alone questions concerning a subject's device preference (question 15) and willingness to continue use (question 16). The first 14 questions in PASAPQ have Likert-type response options of 1 (very dissatisfied) to 7 (very satisfied). Question 15 ask for a response to indicate the preference for the trial device. Question 16 asks for a response between 0 and 100 with 0 indicating not willing to continue using the trial device and 100 indicating definitely willing to continue.

The performance domain score is the sum of 7 questions within the domain (Q1, Q2, Q3, Q4, Q5 Q10 and Q11) and then transformed to a 0 (least) to 100 (most) point scale.

5.1.2 Secondary endpoints

Total score of PASAPQ:

Total score domain containing 13 questions will be evaluated at Visit 3 (week 4) and Visit 4 (week 8).

The proportion of patients indicating preference:

Preference for either inhalation device will be evaluated at Visit 4 (week 8).

Overall Satisfaction Question Score from PASAPQ:

The answer to the PASAPQ question "Overall, how satisfied are you with your inhaler" measured using a 7-point Likert scale (1 meaning very dissatisfied and 7 means very satisfied) at Visit 3 (week 4) and Visit 4 (week 8).

Willingness to continue:

Question 16 asks for a response between 0 and 100 with 0 indicating not willing to continue using the trial device and 100 indicating definitely willing to continue, which will be evaluated at Visit 4 (week 8).

5.2 ASSESSMENT OF SAFETY

5.2.1 Physical examination

A full physical examination will be completed on all patients at screening (Visit 1) and Visit 4. All clinically relevant abnormal findings at the screening visit will be recorded on the Medical History/Baseline Conditions eCRF page. Clinically relevant new abnormal findings or worsening of baseline conditions detected at follow-up physical examinations will be recorded as AEs on the appropriate eCRF page. All (S)AEs, including those persisting after individual patient's end of trial must be followed up until they have resolved, have been assessed as 'chronic' or 'stable', or no further information can be obtained.

5.2.2 Vital signs

Pulse rate and blood pressure will be measured and recorded at screening Visit 1 and Visit 4.

Vital Status for patients who discontinue early:

The objective of obtaining vital status is to ascertain information on health status in patients who withdraw prematurely from randomized treatment up to the previously projected exit date from the trial. Depending on the time of discontinuation, there will be 1 or 2 calls made to the patients to assess their vital status. The site must make at least 2 attempts to contact the patient at each projected time point. The following information should be obtained during these phone calls: 1) date of follow up; 2) status (alive, deceased or lost to follow up); if lost to follow up, last date known alive, if patient is deceased the date and cause of death must be recorded. In this case the site must complete and forward an SAE form to [REDACTED]

[REDACTED] and the reason for lost to follow up should be recorded.

5.2.3 Safety laboratory parameters

Clinical laboratory testing will be conducted on all patients at the Screening Visit (Visit 1) and (Visit 4).

Laboratory specimens (blood and urine) will be collected in the morning with the patient having fasted for at least 8 hours. The patient may have a light snack after blood collection on these pulmonary function test-days.

Hematology testing will include hemoglobin, hematocrit, erythrocytes, platelets, total leukocyte count with differential (neutrophils, lymphocytes, monocytes, eosinophils, and basophils), and absolute eosinophil count. Serum chemistry testing will include albumin, alkaline phosphatase, calcium, chloride, creatinine, glucose, inorganic phosphorus, LDH, potassium, AST (SGOT), ALT (SGPT), sodium, total bilirubin, total protein, uric acid, urea nitrogen (or urea).

The urinalysis will include specific gravity, pH, glucose, protein, leukocytes and erythrocyte.

A urine pregnancy test will be conducted at the screening visit and visit 4 in all women of child-bearing potential.

Proprietary confidential information © 2020 Boehringer Ingelheim International GmbH or one or more of its affiliated companies

All clinical laboratory tests will be performed at local laboratory. Comments should be given for each value considered clinically relevant (for instance, outside the reference range or if any value that differs importantly from previous ones). If the baseline laboratory evaluation is repeated, only the most recent results are used for evaluation of patient participation. The significant abnormality as judged by the investigator will be recorded as adverse events.

5.2.4 Electrocardiogram

A standard 12-lead electrocardiogram (ECG) will be recorded as scheduled in the flowchart. The investigator or a designee will evaluate whether the ECG is normal or abnormal and whether it is clinically relevant, if abnormal.

All electrocardiograms should be performed prior to pulmonary function. The interpretation of the ECG will be performed by the investigator or a qualified designee.

The purpose of the baseline ECG (Visit 1) is to obtain information about the patient's baseline condition that may have not been elicited in obtaining the medical history; therefore, any significant findings from this examination are recorded on the Medical History/Concomitant Diagnoses page.

The purpose of the ECG at Visit 4 is to find any new condition or worsening on baseline condition. Clinically relevant abnormal findings should be reported as an adverse event.

If necessary, additional ECGs may be recorded for safety reasons. Dated and signed printouts of ECG with findings should be documented in patient's medical record.

5.2.5 Other

Medical History

A complete medical history by body system will be performed on all patients at the screening visit. All active and resolved historical disorders for the last 5 years will be recorded on the eCRF.

Record of Investigational Drug

A paper Patient Diary will be kept documenting the administration of the investigational drug during the study.

Concomitant Therapies

All concomitant therapies taken in the 2 months preceding the screening visit and throughout the study (including baseline period) will be recorded on the Concomitant Therapy eCRF page.

Smoking Status

The smoking status (current smoker or ex-smoker) of each patient will be recorded at the screening visit (Visit 1).

5.2.6 Assessment of adverse events

5.2.6.1 Definitions of AEs

5.2.6.1.1 Adverse event

An AE is defined as any untoward medical occurrence in a patient or clinical investigation subject administered a medicinal product and which does not necessarily have to have a causal relationship with this treatment.

An AE can therefore be any unfavourable and unintended sign (including an abnormal laboratory finding), symptom, or disease temporally associated with the use of a medicinal product, whether or not considered related to the medicinal product.

The following should also be recorded as an AE in the CRF and BI SAE form (if applicable):

- Worsening of the underlying disease or of other pre-existing conditions
- Changes in vital signs, ECG, physical examination and laboratory test results, if they are judged clinically relevant by the investigator.

If such abnormalities already exist prior to trial inclusion, they will be considered as baseline conditions and should be collected in the eCRF only.

5.2.6.1.2 Serious adverse event

A serious adverse event (SAE) is defined as any AE, which fulfils at least one of the following criteria:

- results in death,
- is life-threatening, which refers to an event in which the patient was at risk of death at the time of the event; it does not refer to an event that hypothetically might have caused death if more severe,
- requires inpatient hospitalisation,
- requires prolongation of existing hospitalisation,
- results in persistent or significant disability or incapacity,
- is a congenital anomaly / birth defect,
- is deemed serious for any other reason if it is an important medical event when based on appropriate medical judgement which may jeopardise the patient and may require medical or surgical intervention to prevent one of the other outcomes listed in the above definitions. Examples of such events are intensive treatment in an emergency room or at home for allergic bronchospasm, blood dyscrasias or convulsions that do not result in hospitalisation or development of dependency or abuse.

5.2.6.1.3 AEs considered “Always Serious”

Cancers of new histology and exacerbations of existing cancer must be classified as a serious event regardless of the time since discontinuation of the drug and must be reported as described in [5.2.6.2](#), subsections “AE Collection” and “AE reporting to sponsor and timelines”.

Proprietary confidential information © 2020 Boehringer Ingelheim International GmbH or one or more of its affiliated companies

In accordance with the European Medicines Agency initiative on Important Medical Events, Boehringer Ingelheim has set up a list of further AEs, which by their nature, can always be considered to be “serious” even though they may not have met the criteria of an SAE as defined above.

The latest list of “Always Serious AEs” can be found in the eDC system. A copy of the latest list of “Always Serious AEs” will be provided upon request. These events should always be reported as SAEs as described above.

5.2.6.1.4 Adverse events of special interest

The term adverse events of special interest (AESI) relates to any specific AE that has been identified at the project level as being of particular concern for prospective safety monitoring and safety assessment within this trial, e.g. the potential for AEs based on knowledge from other compounds in the same class. AESIs need to be reported to the sponsor’s Pharmacovigilance Department within the same timeframe that applies to SAEs, please see [section 5.2.6.2.2](#).

The following are considered as AESIs:

Hepatic injury

A hepatic injury is defined by the following alterations of hepatic laboratory parameters:

- An elevation of AST (aspartate transaminase) and/or ALT (alanine aminotransferase) ≥ 3 fold Upper Level of Normal (ULN) combined with an elevation of total bilirubin ≥ 2 fold ULN measured in the same blood draw sample, or
- Aminotransferase (ALT, and/or AST) elevations ≥ 10 fold ULN.

These lab findings constitute a hepatic injury alert and the patients showing these lab abnormalities need to be followed up according to the “DILI checklist” provided in the ISF. In case of clinical symptoms of hepatic injury (icterus, unexplained encephalopathy, unexplained coagulopathy, right upper quadrant abdominal pain, etc.) without lab results (ALT, AST, total bilirubin) available, the investigator should make sure these parameters are analysed, if necessary in an unscheduled blood test. Should the results meet the criteria of hepatic injury alert, the procedures described in the DILI checklist should be followed.

